¹²Between Visits 2 and 4, participants will be asked to record daily any symptoms which they think may be related to hypocalcemia (paresthesias, muscle cramps, etc). They will be asked to describe the symptoms and mark the time that the symptoms occurred and the severity of the symptoms (graded on a scale of 1-5). They will record the doses of calcium administered and how long it took the symptoms to resolve. Participants will total their daily calcium intakes. They will be instructed to contact us if they are requiring greater than 8 g /day and in such instances will be started on calcitriol 0.25 mcg twice daily to increase their intestinal calcium absorption.

¹³Randomization only performed for patients receiving total thyroidectomy with histologically confirmed diagnosis of PTC and no evidence of metastases.

¹⁴Only patients with histologically confirmed cancer diagnosis. Consult will occur at approximately two weeks after surgery for patients who receive total thyroidectomy and at approximately six to eight weeks after surgery for those who receive partial thyroidectomy.

¹⁵Thyroglobulin determinations will also include anti-thyroglobulin antibody.

¹⁶An unstimulated thyroglobulin level will be obtained at Week 6 to assist in decision making regarding the necessity for radioactive iodine ablation therapy.

¹⁷Randomization patients only. Patients enrolled into the standard of care arm will not receive special labs for research only.

Table of Contents

Summary.....	2
Trial overview diagram.....	3
Schedule of activities	4
List of abbreviations and definitions.....	6
1. Introduction.....	8
1.1. Background.....	8
1.2. Rationale and hypothesis	9
2. Objectives.....	9
2.1. Primary outcome and endpoints.....	9
2.2. Secondary outcomes and endpoints	10
3. Study design	11
4. Study population.....	16
4.1. Inclusion criteria	16
4.2. Exclusion criteria.....	16
4.3. Intra-operation exclusion criteria.....	16
4.4. Protected populations	16
5. Trial interventions.....	16
5.1. Treatment Arm 1, Group 1 (No CND)	16
5.2. Treatment Arm 2, Group 2 (CND).....	16
5.3. Allocation to intervention.....	16
6. Participant recruitment and consent.....	17
6.1. Participant identification	17
6.2. Screening	17
6.3. Recruitment and consent	17
7. Activities and measurements.....	18
7.1. Table: Time points for data collection.....	19
7.2. Blood sample collection.....	21
7.3. Data entry.....	21
7.4. Participant withdrawals.....	21
7.5. Stopping rules	22

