2.1. Primary outcome and endpoints

To determine the rate of transient and permanent hypocalcemia:

- Transient hypoparathyroidism as defined by a Day 1 serum parathyroid hormone (PTH) level of <10 pg/ml
- Post-operative serum calcium (mg/dL) and PTH (pg/ml) at Day 12 and Month 6

- Total calcium consumption in first 2 weeks (total gm)
- Hypocalcemia symptoms in first 2 weeks (average episodes/day)
- Hypocalcemia symptom severity scale (range of 1-5)
- Requirement for calcium and calcitriol at Month 6 (or, if laboratory values at visit reveal calcium < 8 mg/dL and PTH <15 pg/ml)

Calcium and PTH levels, calcium intake, and hypocalcemia symptoms will be monitored post-operatively (at Day 1, Day 12, and Month 6) to examine how parathyroid function is affected by a CND.

Hypoparathyroidism can lead to paresthesias and muscle cramps and is a known complication of total thyroidectomy, requiring frequent treatment with calcium and vitamin D. This risk is increased with a CND and is thus important to quantify when examining the risk/benefit ratio. Because calcium supplementation is routinely administered for symptoms of hypocalcemia in the post-operative period and this may impact the interpretation of laboratory evaluations, we will be evaluating a variety of metrics to assess the incidence and impact of hypocalcemia on patients.

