Post-operative follow-up: Post-operative follow-up will be done in the hospital on post-operative Day 1, and clinic follow up will occur at Day 12, Week 6, Month 6, and 1 Year. Patients will be discharged with thyroid hormone that will be administered at 1.5-1.7 mcg/kg daily. Patients will be provided a hypocalcemia symptom log and will be requested to record their calcium intake and symptoms daily. When they have symptoms they will be asked to record the time of the symptoms, what the symptoms were, the severity of the symptoms (scale of 1-5), the amount of calcium taken to treat the symptoms, and the time to symptom resolution.

All patients will be seen in follow up in the clinic in approximately 2 weeks. A calcium and PTH level will be obtained at that visit. Patients will be asked about their calcium intake and their symptoms of hypocalcemia, and their symptom log will be reviewed by study staff (Aim 1). Their symptom log will be collected at the two-week appointment and abstracted by study staff to determine the total volume of calcium supplementation consumed, the type and frequency of hypocalcemia symptoms, and the severity of those symptoms when they occurred.

Comprehensive voice and swallow⁵ evaluations will also be performed at the Day 12 visit, and these evaluations will be repeated at Week 6, Month 6, and 1 Year visits (Aim 2) if abnormalities or complaints were noted at the previous time point. All of the voice assessments listed in section 2.2 are part of a standard voice evaluation which is done routinely for patients with a history of previous neck surgery or any voice concerns, either pre-operatively or post-operatively. The video swallow exam is normally only done if there are concerns with voice or swallow function post-operatively. If deficits are observed at Day 12, appropriate treatment will be provided. This may include watchful waiting, behavioral therapy, diet modification, use of injectables, or further surgery. Follow-up assessments at Week 6, Month 6, and 1 Year will, in these cases, provide preliminary data on treatment outcomes. Patients will also complete QOL surveys and interviews to determine the effects (if any) of post-operative complications on overall well-being at each visit (Aim 3).

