Post-operative care in hospital: After surgery, participants will remain in the hospital overnight per surgeon preference and laboratory evaluations will be performed per standard of care.

Post-operative Day 1: The participant will be educated on the signs and symptoms of hypocalcemia and be given detailed instruction on how to treat these symptoms per standard of care. They will be given a study log to fill out which will allow them to record the frequency and severity of symptoms and the number of doses of calcium taken. This will be completed and returned to study staff at the Day 12 visit.

Day 12 visit: Physical and laboratory evaluations will be performed per standard of care. A comprehensive voice and swallow⁵ evaluation will be conducted; this will be considered a research procedure unless the participant is experiencing difficulty swallowing or there is evidence of vocal fold dysfunction. The participant will also complete a QOL survey and participate in a qualitative interview per study protocol.

Week 6 visit: 48 hours prior to the Week 6 visit day, participants will have a blood sample drawn to establish post-operative thyroglobulin levels and assess response to treatment. During the visit, participants will complete QoL surveys and participate in a qualitative interview. If the patient's voice or swallow function was impaired at the Day 12 visit, additional voice and swallow⁵ evaluations will also be performed.

At this time the treating endocrinologist will assess the subject's risk profile based on the criteria outlined in section 3 of the protocol. If the patient is classified as intermediate- or high-risk or if the patient is classified as low-risk but chooses to undergo RAI remnant ablation, he or she will be treated according to the following standard schedule:

- Day 1: rTSH injection
- Day 2: rTSH injection
- Day 3: 50 mCu I-131 therapy administered²
- Day 5: Stimulated thyroglobulin lab
- Day 5-17: Whole Body Scan performed

Month 6 visit: Physical and laboratory evaluations, as well as an ultrasound of the neck, will be performed per standard of care. PTH and calcium samples required for the study will be drawn at this time. A QOL survey and qualitative interview will be completed. If the patients' voice or swallow function was impaired at the Week 6 visit, additional voice and swallow⁵ evaluations will also be performed.

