8.2. Analysis of endpoints

For all primary aims, data will be analyzed using a mixed model two-way analysis of variance examining the effects of treatment group, time and factor interactions, such as radioactive iodine dose. Evaluation time periods (pre-surgery, Day 12, Week 6, Month 6, and 1 Year) will serve as between subjects factor and treatment group (prophylactic CND versus no CND) will serve as the between subjects factor. Experiment-wise error will be controlled with an appropriate adjustment to the alpha-level. Prior to each analysis, we will plot all data and carefully examine each analysis to ascertain that the assumptions of ANOVA are not violated. Data will be transformed as necessary to better conform to the assumptions. Nonparametric statistics will be used when assumptions for ANOVA are not achieved. Statistical support for the study design and analysis will be performed by [name] who will perform analyses with SAS statistical software (SAS Institute Inc., Cary, NC).

9. Risks and benefits of trial participation

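### The two-week calcium total comes from a log that stops at a Day 12 ± 8 day visit, so it partly measures visit timing

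*Combined protocol and SAP*

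**What the plan says.** Section 2.1 (Primary outcome and endpoints) lists "Total calcium consumption in first 2 weeks (total gm". The next bullet, drawn from the same log, is scaled by time: "Hypocalcemia symptoms in first 2 weeks (average episodes/day".

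The log is the only stated source of the total. Footnote 12 of the Schedule of activities has it run between Visits 2 and 4 and adds: "Participants will total their daily calcium intakes". Section 7 (Post-operative Day 1) says of the log: "This will be completed and returned to study staff at the Day 12 visit". Section 3 (Post-operative follow-up) says: "Their symptom log will be collected at the two-week appointment and abstracted by study staff to determine the total volume of calcium supplementation consumed". The same section gives the nominal timing: "All patients will be seen in follow up in the clinic in approximately 2 weeks". The window row of the Schedule gives Visit 4, labelled Day 12, a tolerance of 8 days either side.

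Section 8.2 says of all primary aims that "data will be analyzed using a mixed model two-way analysis of variance". It has no term or rule for log length. Section 3 (Blinding) counts calcium intake among the secondary endpoints, although section 2.1 places it under primary.

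**The concern.** The endpoint names a two-week period, but observation ends on whatever day the visit takes place. Two patients with the same daily intake can therefore record different totals because one was seen sooner. The documents do not say that entries after Day 14 are dropped, that the log continues after an early visit, that the total is divided by days logged, or how a short log is treated. An analyst following the plan as written would compare sums over unequal periods.

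The stake is precision. Variation in visit day is added to variation in calcium need, which makes a real difference between arms harder to see on this measure.

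**Working it through.** **The plan's own figure.** The plan gives no sample size or precision for the calcium total. Its only computed size is 116 (58 per arm) for transient hypoparathyroidism, 12% against 36%, at power 0.8 and alpha 0.05. A two-sided continuity-corrected calculation gives 57 per arm, 114 in all, close to that figure. It concerns Day 1 PTH, and nothing below bears on it.

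**Log length.** From the Schedule, 12 − 8 = 4 days to 12 + 8 = 20 days. This is approximate by about a day, because footnote 12 starts the log at Visit 2 while section 7 hands it out on post-operative Day 1. An on-time visit gives 12 of the 14 named days.

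**Range of totals.** Total = daily intake × days logged, with intake assumed constant. At an assumed 3 g/day:
- Cut at Day 14: 3 × 4 = 12 g to 3 × 14 = 42 g, a ratio of 14/4 = 3.5.
- No cut: 12 g to 3 × 20 = 60 g, a ratio of 5.

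Patients can even be ranked the wrong way round. The 8 g/day contact level in footnote 12, used here only as an illustration, gives 8 × 4 = 32 g on a 4-day log. That is less than the 42 g from 3 g/day over 14 days.

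**Effect on variance.** Assume that visit day is independent of daily intake, and write CVr for the between-patient CV of daily intake and CVd for the CV of log length. The squared CV of the total, relative to that of a fixed period, is

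(CVr² + CVd² + CVr²·CVd²) / CVr² = 1 + CVd²/CVr² + CVd².

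The documents do not give the spread of visit days, so two spreads are assumed, both cut at Day 14:

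| Assumed visit days | Mean log (days) | SD | CVd | Ratio, CVr = 1.0 | Ratio, CVr = 0.75 | Ratio, CVr = 0.5 |
|---|---|---|---|---|---|---|
| Even over Days 4–20 | 10.76 | 3.49 | 0.32 | 1.21 | 1.29 | 1.53 |
| Even over Days 8–16 | 11.67 | 2.16 | 0.19 | 1.07 | 1.10 | 1.17 |

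For example, with CVd² = 0.105 and CVr = 0.5, the ratio is 1 + 0.105/0.25 + 0.105 = 1.53.

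**If intake tapers.** Assume 3 g/day on the first day, halving every 5 days:

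| Days logged | Total (g) | Grams per logged day |
|---|---|---|
| 4 | 9.9 | 2.47 |
| 8 | 15.5 | 1.94 |
| 12 | 18.8 | 1.57 |
| 14 | 19.8 | 1.42 |

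The total now varies 19.8/9.9 = 2.0-fold, less than under constant intake. Grams per logged day varies 2.47/1.42 = 1.74-fold in the opposite direction. Over the even Day 4–20 spread cut at Day 14, the CV due to timing alone is 0.18 for the total and 0.20 for grams per logged day. Dividing by days logged therefore does not remove the artefact when intake falls over time.

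**The case against.** The strongest reply is that the label already limits the period. Because participants total their calcium each day, staff can discard entries after Day 14. That is a fair reading, and it is why the size here rests on the 3.5-fold range and not the 5-fold one. But the cut is not written down, and it cannot restore days lost to an early visit.

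Second, constant intake is an assumption. The hypoparathyroidism at issue is mostly transient (for total thyroidectomy, section 8.1 gives 12% transient against 1–2% permanent), so need probably declines and the distortion shrinks. This stands. It also counts against grams per logged day as the remedy.

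Third, a permitted window is not an observed spread. With visits planned at about two weeks, most may cluster and the loss would be smaller. This stands too.

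A reader might infer that the arm seen earlier would show a falsely low total, biasing the comparison towards no harm. The documents do not support that. Allocation is randomised, participants are blinded until this visit, and no text ties visit timing to arm or symptoms. Nor should the variance factor be turned into a loss from 58 per arm: that number was set for Day 1 PTH, and the current plan is to randomise 70 to 140. Finally, this is one of several hypocalcaemia measures, and section 3 calls calcium intake secondary.

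**Conclusion.** The concern holds in a limited form. The total mixes calcium need with visit timing, the stated two weeks are not covered even by an on-time visit, and no rule handles short logs. With a Day 14 cut and constant intake, permitted totals differ 3.5-fold. Under an even spread over the whole window, the relative variance is about 1.2 to 1.5 times that of a fixed period, for a daily-intake CV of 100% to 50%. It is about 1.1 to 1.2 times if visits fall evenly over Days 8–16, and lower again if intake tapers. These sizes rest on assumed intake and visit spreads that the documents do not give.

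The consequence is noise on this one endpoint. Bias would need visit timing to depend on arm or symptoms, which is not shown. The defect is the same whether the endpoint is called primary or secondary.

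**What to change.** Define the endpoint over a fixed, common range of post-operative days, using the daily totals already recorded: for example, from post-operative Day 1 to a day that nearly all logs reach, chosen without reference to arm. Alternatively, have participants keep the log through Day 14 whatever the visit date and return it afterwards. In either case:
- state the day on which the log starts;
- record log length;
- drop entries after Day 14;
- state how logs that do not cover the range are handled;
- report grams per logged day only as a sensitivity analysis, because it also depends on log length when intake tapers.

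Sections 2.1 and 3 should be reconciled on whether calcium intake is primary or secondary.

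The fixed range costs a line of endpoint wording and a derived variable, but a shorter range discards later entries. Keeping the log to Day 14 preserves the two-week period, but some logs must then be returned after the visit. Because participants are unblinded at that visit, their later entries would be made with knowledge of the arm.

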Patients randomized to Arm 2 will be receive total thyroidectomy with an ipsilateral CND. The CND will be performed as described by a consensus conference of the ATA. This will include removal of the prelaryngeal nodes, the pretracheal nodes, and the paratracheal lymph nodes. The paratracheal dissection will be bounded superiorly by the cricoid cartilage and inferiorly by the innominate artery on the right and on the left by the axial plane where the innominate crosses the trachea. The superior parathyroid gland will be preserved in situ along with its primary blood supply from the superior branch of the inferior thyroid artery. The inferior parathyroid gland will be reflected laterally along with its blood supply from the inferior thyroid artery. Parathyroid autotransplantation will be performed if the glands are devascularized during dissection. Paratracheal tissue specimens will be examined for parathyroid glands that may be salvaged and transplanted before being removed from the sterile field. Suspected parathyroid glands will be confirmed by frozen section biopsy prior to autotransplantation.

Blinding: Both surgical procedures are performed through the same incision and post-operative care is identical. As such, the neck dressings are identical, allowing both the patients and study staff to be masked with regard to treatment arm randomization. Participants will remain blinded to treatment arm until the Day 12 follow-up appointment, at which point their pathology report will be reviewed with them, and unblinding will occur. Because subjective symptoms and calcium intake are two of our secondary endpoints, we will minimize participant and researcher bias in the description and treatment of post-operative symptoms in the immediate post-operative period. Because the risks of the two procedures and the post-operative instructions are identical for both arms, there is no risk associated with blinding the patients until their Day 12 follow-up. Participants who screen fail intra-operatively will be notified as to which procedure(s) was conducted immediately following surgery. The surgeon performing the procedure cannot and will not be blinded to the participant's treatment arm at any time.

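### Symptom severity (1-5) is recorded only when symptoms occur and is undefined for symptom-free patients, so an arm comparison on it is not protected by randomisation and may be biased in either direction

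*Combined protocol and SAP*

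**What the plan says.** Section 2.1 (Primary outcome and endpoints) lists "Hypocalcemia symptom severity scale (range of 1-5" on its own line, next to a frequency endpoint, "Hypocalcemia symptoms in first 2 weeks (average episodes/day". It names no per-patient summary of severity, such as mean, worst or per-episode.

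Three places describe how severity is collected:

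- Schedule of activities, footnote 12: for symptoms entered in the daily log, patients note "the severity of the symptoms (graded on a scale of 1-5".
- Section 3, Post-operative follow-up: "When they have symptoms they will be asked to record the time of the symptoms", with severity in the same list of items.
- The same part of Section 3: staff abstract the type and frequency of symptoms "and the severity of those symptoms when they occurred".

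Section 8.2 says "For all primary aims, data will be analyzed using a mixed model two-way analysis of variance", allows nonparametric methods if assumptions fail, and gives no rule for symptom-free patients.

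The rank of the endpoint is inconsistent. Under Blinding, Section 3 reads "Because subjective symptoms and calcium intake are two of our secondary endpoints", and Section 8.1 places the primary endpoint at post-operative day 1.

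**The concern.** A patient with no symptoms generates no grade. Followed as written, the data support a severity comparison only among patients who had at least one symptom. Having a symptom is itself an outcome after randomisation. Section 1.2 hypothesises more complications with CND, and Section 2.1 says that CND raises the risk of hypoparathyroidism, which it links to symptoms. The scored patients in the two arms would then differ in kind, and the contrast between them is not the effect of the randomised procedure.

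At stake is a harm comparison that can mislead. If CND turns some symptom-free patients into mildly symptomatic ones, average severity among the symptomatic falls in the CND arm although nobody is better off. If the added cases are as severe as the others, the extra harm does not show in this measure at all.

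**Working it through.** **The plan's own figure.** The documents give no figure for severity. The nearest is the sample size in Section 8.1: 12% against 36% transient hypoparathyroidism, power 0.8, alpha 0.05, 58 per arm, 116 in total. A two-sided two-proportion calculation gives 49 per arm uncorrected and 57 per arm (114) with continuity correction, close to the stated figure. That calculation rests on the Day 1 laboratory endpoint, so the present point does not affect it.

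**Inputs.** The 12% and 36% are borrowed as stand-in symptom rates; in the documents they are rates of a Day 1 PTH outcome. All severity means below are assumptions.

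**Formulas.** Let s1 and s2 be the shares with symptoms without and with CND. Let a be the mean grade of patients who would have symptoms under either operation, taken as equal in both arms, and b the mean grade of the cases that CND adds.

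- Symptomatic-only means: a without CND; [s1·a + (s2 − s1)·b]/s2 with CND. Difference: (s2 − s1)(b − a)/s2.
- All-patient means with symptom-free = 0: s1·a without CND; s1·a + (s2 − s1)·b with CND. Difference: (s2 − s1)·b.

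The sign of the first difference depends only on whether b is below or above a. The second is positive whenever CND adds cases.

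**Results with s1 = 0.12, s2 = 0.36, a = 3:**

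| b | Symptomatic only, no CND vs CND | All patients, no CND vs CND |
|---|---|---|
| 1 | 3.00 vs 60/36 = 1.67 | 0.36 vs 0.60 |
| 2 | 3.00 vs 84/36 = 2.33 | 0.36 vs 0.84 |
| 3 | 3.00 vs 108/36 = 3.00 | 0.36 vs 1.08 |
| 4 | 3.00 vs 132/36 = 3.67 | 0.36 vs 1.32 |

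**Sensitivity to the assumed symptom rates, with a = 3.5 and b = 2:**

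| s1 / s2 | Symptomatic-only difference | All-patient difference |
|---|---|---|
| 12% / 36% | −1.00 | +0.48 |
| 12% / 51% | −1.15 | +0.78 |
| 30% / 50% | −0.60 | +0.40 |
| 50% / 70% | −0.43 | +0.40 |
| 70% / 80% | −0.19 | +0.20 |

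**Patients with a score.** At 12%/36%: 0.12 × 58 = 7 vs 0.36 × 58 = 21, or 0.12 × 35 = 4 vs 0.36 × 35 = 13 at the lower end of the current 70-140 range. At 70%/80% and 58 per arm: 41 vs 46.

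**Simulation.** 4,000 trials per setting, grade = 1 + Binomial(4, p), Mann-Whitney test at 0.05.

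| Setting | n per arm | Symptomatic-only test: CND significantly milder | All patients, symptom-free = 0: CND significantly worse |
|---|---|---|---|
| 12%/36%, a = 3.5, b = 2 | 58 | 47% | 80% |
| 12%/36%, a = 3.5, b = 2 | 35 | 25% | 58% |
| 40%/60%, a = 3.5, b = 2 | 58 | 36% | 29% |
| 12%/36%, a = b = 3 | 58 | 2% | 86% |
| 12%/36%, a = 3, b = 4 | 58 | 0% | 91% |

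**The case against.** The strongest reply is that the plan is silent rather than wrong. It does not specify a mean among symptomatic patients and excludes nobody. The scale anchors and the log form are not in the documents, so coding no symptoms as 1 is not formally ruled out. That stands as far as it goes: a reader might infer that a symptomatic-only mean is the planned analysis, and the text does not say so. But every description of collection ties the grade to a symptom that occurred, and nothing supports any value for the others. The symptomatic-only comparison is the natural result of following the text.

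Second, a reader might infer that the measure always favours CND. The documents do not support this. Nothing in them says that CND-induced symptoms are milder, and the table shows the difference vanishing at b = 3 and turning against CND at b = 4.

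Third, a reader might infer that most of the sample drops out. That needs the Day 1 PTH rates to be symptom rates, and the documents give no symptom rates.

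Fourth, severity will not be read alone. Episodes per day can be zero for a symptom-free patient and total calcium intake can be defined for everyone, so added mild cases would show there. This is real mitigation. It does not repair a separately listed severity comparison, which could contradict those endpoints for reasons unrelated to any benefit.

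Finally, the label primary is contestable, given Section 3 (Blinding) and Section 8.1. That bears on how much weight the endpoint carries, not on the selection problem.

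**Conclusion.** The point holds as a defect in how the endpoint is defined. Severity has no value for symptom-free patients, so the natural arm comparison is conditional on a post-randomisation outcome that the trial expects CND to alter. Confidence is high on that.

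The direction and size of the bias are not known. They depend on the symptom rates and on how severe the added cases are, and the documents give neither. Under the assumed 12%/36% with milder added cases (3 and 2), the sign reverses: 3.0 vs 2.33 among symptomatic patients against 0.36 vs 0.84 over all patients. With equally severe added cases the symptomatic-only difference is zero; with more severe ones CND looks worse. The arithmetic also assumes that patients symptomatic without CND would have the same severity with it, and it counts a symptom-free patient as 0.

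The sample size is unaffected. The change should be made before the severity data are compared by arm.

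**What to change.** In Section 2.1, define severity for every randomised patient as the worst grade over the log period on a 0-5 scale, with 0 meaning no symptoms and 1-5 as now. In Section 8.2, name a rank-based test for the arm comparison; that section already allows nonparametric methods. Report severity among symptomatic patients descriptively only.

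State when a 0 may be assigned: only if the log was returned and absence of symptoms is confirmed, by log entries or at the two-week log review with the patient. That question is best asked before the pathology report is discussed, because unblinding happens at the same visit. Treat unfilled days and unreturned logs as missing. Section 7.4 anticipates non-adherence to the Symptom Log, so reading every blank day as 0 would create false zeros. Report the number of incomplete and missing logs by arm.

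Reconcile Section 2.1 with Section 3 (Blinding) and Section 8.1 on whether symptom endpoints are primary or secondary.

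The cost is a line each in Sections 2.1 and 8.2 and an added item on the abstraction form, with no new visits or tests. The downsides are a skewed score with many zeros, which a rank test tolerates, and some ambiguity in logs already collected with blank days.
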